### **5.6.2. Adverse Events**

The verbatim terms used in the CRF by investigators to identify adverse events will be coded using the Medical Dictionary for Regulatory Activities (MedDRA version 21.1 or higher). Any AE occurring at or after the initial administration of study intervention is considered to be treatment emergent. If the event occurs on the day of the initial administration of study intervention, and either event time or time of administration are missing, then the event will be assumed to be treatment emergent. If the event date is recorded as partial or completely missing, then the event will be considered to be treatment emergent unless it is known to be prior to the first administration of study intervention based on partial onset date or resolution date. All reported treatment-emergent adverse events will be included in the analysis. For each adverse event, the number and percentage of participants who experience at least 1 occurrence of the given event will be summarized by intervention arm.

Summary tables will be provided for treatment-emergent adverse events:

- AEs
- Serious AEs (SAEs)
- AEs leading to discontinuation of any study agent within a study intervention including NA
- AEs by relationship to each study agent within a study intervention including NA
- AEs leading to dose interruption/dose modification of each study agent within a study intervention.

In addition to the summary tables, listings will be provided for participants who:

- Had SAEs
- Had AEs leading to discontinuation of each study agent withing a study intervention including NA

For participants reporting rash, a listing with specific grade will be provided.

Incidence of treatment-emergent adverse events of special interest will be summarized by analysis phase and overall

The adverse events of special interest include:

- ALT/AST elevations
- Injection Site Reactions Related to JNJ-3989 and/or PegIFN- $\alpha$ 2a

- Renal Complications
- Hematologic Abnormalities (platelet count, hemoglobin, reticulocytes, neutrophil count)

The list of all preferred terms belonging to ALT/AST elevation, renal complications, and hematologic abnormalities is provided in [Appendix 8](#). Injection site reactions will be identified using the eCRF Injection Site Reaction form.

A listing of participants who died will be provided.

### 5.6.3. Additional Safety Assessments

#### 5.6.3.1. Clinical Laboratory Tests

Laboratory data will be summarized by category of laboratory test. The different categories and laboratory tests used in the analysis are listed in [Table 7](#).

**Table 7: Laboratory Parameters**

Laboratory Assessments	Parameters		
Hematology	Platelet count Red blood cell count Hemoglobin Hematocrit	RBC Indices: MCV MCH % Reticulocytes	White Blood Cell (WBC) count with Differential: Neutrophils Lymphocytes Monocytes Eosinophils Basophils
Hematology Coagulation	Activated partial thromboplastin time Prothrombin Intl. normalized ratio Prothrombin time		
Clinical Chemistry	Sodium Potassium Chloride Bicarbonate Blood urea nitrogen (BUN) Creatinine Cystatin C Glucose Aspartate aminotransferase (AST) Alanine aminotransferase (ALT) Gamma-glutamyltransferase (GGT) $\alpha_1$ -acid glycoprotein Fibrinogen (on blood) eGFR calculation based on Creatinine (by CKD EPI formula, eGFRcr) eGFR calculation based on Cystatin C (by CKD EPI formula, eGFRcys)	Total, direct, indirect bilirubin Alkaline phosphatase Creatine phosphokinase (CPK) Lactic acid dehydrogenase (LDH) Uric acid Calcium Phosphate Albumin Total protein Total cholesterol High-density lipoprotein cholesterol Low-density lipoprotein cholesterol Triglycerides Magnesium Lipase Amylase (reflex testing of pancreatic amylase should be done in case of amylase or lipase increase from screening onwards)	

Laboratory Assessments	Parameters	
Routine Urinalysis	Dipstick Specific gravity pH Glucose Protein Blood Ketones Bilirubin Urobilinogen Nitrite Leukocyte esterase	Sediment (if dipstick result is abnormal) Red blood cells White blood cells Epithelial cells Crystals Casts Bacteria
	In case of a positive dipstick result, a urine sample will be set aside for additional examination of the positive parameter (e.g. quantification as applicable).	
Urine Chemistry (quantitative measurement)	Creatinine Sodium Phosphate	Glucose Protein Albumin
Renal Biomarkers	Retinol binding protein a Beta-2-microglobulin a Note: Other biomarkers might be measured.	

Clinical laboratory tests will be displayed for the participants included in the safety analysis set.

Descriptive statistics and graphical displays will be presented for all chemistry, hematology, and urinalysis laboratory tests at scheduled time points.

Change from baseline over time will be summarized for chemistry, hematology, urinalysis tests and renal biomarkers and displayed.

Abnormality criteria (based on the criteria specified in the DAIDS Toxicity Grade Scale (see Clinical Protocol Appendix 9, DAIDS table)) will be applied to baseline and postbaseline values or in accordance with the normal ranges of the clinical laboratory if no gradings are available.

Postbaseline abnormalities will be compared with their corresponding baseline result:

- For toxicity grades, treatment emergent (TE) will be concluded if the postbaseline grade is worse than the baseline grade.
- For abnormalities based on normal range and/or criteria: If the postbaseline value is above the upper limit and the baseline value is below the upper limit (e.g. Normal or Low), then the postbaseline abnormality will be considered TE. The same applies to the postbaseline value being below the lower limit with the baseline value being above the lower limit (e.g. Normal or High).
- If the baseline value is missing, a postbaseline abnormality will always be considered as TE.

For each lab parameter, a worst-case analysis will be performed by using the worst abnormality and/or worst toxicity grade lab value and time point per participant. The worst toxicity case is the value associated to the highest toxicity grade and is derived per parameter and toxicity direction

(hypo/hyper). Worst-case will be derived withing each analysis phase, including unscheduled assessments. For abnormalities, in case the same participant has both abnormalities (low and high) for the same lab test within the same phase, the participant will be counted in the analysis for both toxicity directions (abnormally high and low).

In case continuous laboratory results are not numerically expressed, but as a character (e.g. 'less than 2', '>25'), these results will be numerically imputed as follows:

- If the analysis result contains '<' then the result will be multiplied by 0.999 (e.g. <6.1 becomes 6.0939).
- If analysis result contains '>' then the result will be multiplied by 1.001 (e.g. >6.1 becomes 6.1061).
- If analysis result contains '≤' or '≥' then only the numeric portion of the result will be used.

This also applies to normal limits expressed as such.

Shift tables will be provided summarizing the shift in laboratory values from baseline over time with respect to abnormality criteria (low, normal, high) for each laboratory parameter by analysis phase.

The cross-tabulations of the worst toxicity grades over time versus baseline grade and the worst abnormalities versus baseline grade per parameter and per analysis phase will be presented including also the number of participants per worst grade and the number of participants per abnormality.

A tabulation of percentage and number of the participants who have treatment-emergent worst toxicity grades and treatment-emergent worst abnormalities per parameter and analysis phase will be included. The incidence table of worst toxicity grade abnormality in laboratory parameters will be also presented stratified by the subgroups of interest identified in Section 5.7.7.2.

Plots of mean (+/- SE) values and changes from baseline over time for selected laboratory parameters will be presented by intervention arm. Spaghetti-plots for selected laboratory parameters will be presented over time by intervention arm (with Week shown on x-axis).

A listing including all parameters with at least one treatment-emergent toxicity or abnormality per participant (exclusion of urinalysis) will be generated.

### **5.6.3.2. Renal Safety**

Renal safety parameters include the urine creatinine, serum creatinine, urine glucose total urine protein, total urine protein, total urine albumin, urine protein to creatinine ratio (UPCR), urine albumin to creatinine ratio (UACR), retinol binding protein (RBP), beta-2-microglobulin, RBP to creatinine ratio, beta-2-microglobulin to creatinine ratio, urine fractional excretion of phosphate (FEPO4), Cystatin C, eGFR based on Creatinine (eGFRcr), eGFR based on Cystatin C (eGFRcys).

Descriptive statistics (n, mean, SD, minimum, median, and maximum) will be calculated for each parameter for observed values and changes from baseline at each scheduled time point by intervention arm and analysis phase. Descriptive statistics will also be calculated by subgroups (eGFRcr Grade  $\geq 3$  [at least once during the treatment period] vs Grade  $< 3$ , confirmed eGFRcr Grade  $\geq 3$ , Type of NA at Baseline).

Plots of mean ( $\pm$  SE) values and changes from baseline over time for the renal safety parameters will be presented overall, and by subgroups (eGFRcr Grade  $\geq 3$  [at least once during the treatment period] vs Grade  $< 3$ , confirmed eGFRcr Grade  $\geq 3$ , Type of NA at Baseline).

A confirmed eGFRcr Grade  $\geq 3$  is defined as a Grade 3 or higher at 2 consecutive post-baseline measurements or an abnormality observed at 1 measurement followed by study drug discontinuation.

A listing including all renal safety parameters for participants with at least one treatment-emergent eGFRcr Grade 3 or higher will be generated. Another listing will be generated with renal safety parameters for participants who had a confirmed eGFRcr Grade 3 or higher.

The analyses will be also performed using subgroups based on eGFRcys.

#### **5.6.3.2.1. eGFR**

Stages of eGFR at baseline versus the minimum post-baseline eGFR value and the last available value will be summarized by count and percent of participants. Kidney disease stages are defined as follows: 1 (Normal): eGFR  $\geq 90$ ; 2 (Mild): eGFR 60-89; 3 (Moderate): eGFR 30-59; 4 (Severe): eGFR  $< 30$ . The following analyses will be done for both eGFRcr and eGFRcys

In addition to the above, the number and proportion of participants with a 10- $< 30\%$ , 30- $< 50\%$  and  $\geq 50\%$  decrease from baseline will be tabulated.

Scatter plots of eGFR versus other renal biomarkers (total urine protein, total urine albumin, urine protein to creatinine ratio [UPCR], urine albumin to creatinine ratio [UACR], retinol binding protein (RBP) and beta-2-microglobulin, RBP to creatinine ratio and beta-2-microglobulin to creatinine ratio, and urine fractional excretion of phosphate [FEPO4]) as well as spaghetti plots will be presented.

In addition, cystatin C assessment is being performed as part of this study. eGFRcys will also be calculated by using the CKD-EPI cystatin C equation.

Differences between the two types of GFR calculation will be assessed. Cross-tabulation of eGFRcr ( $< 10\%$ , 10- $< 30\%$ , 30- $< 50\%$  and  $\geq 50\%$  decrease from baseline) versus eGFRcys ( $< 10\%$ , 10- $< 30\%$ , 30- $< 50\%$  and  $\geq 50\%$  decrease from baseline) will be presented over time.

### 5.6.3.2.2. Proximal Renal Tubular Function

#### Proteinuria by Quantitative Assessment

Total urine protein, total urine albumin, UPCR and UACR will be summarized by intervention arm and visit using descriptive statistics.

The number and proportion of participants with UACR and UPCR results in the following categories over time will be tabulated:

- UACR: < 30, ≥ 30 to 300, >300 mg/g
- UPCR: < 200 mg/g versus ≥ 200 mg/g

Median (Q1, Q3) percent change from baseline over time will be plotted by intervention arm.

The evolution over time of total urine protein and total urine albumin will also be presented.

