Visit Day (D)/Week (W)	W 4 to 0 ^e	W0/ D1	W2 ^f	W4	W8	W12	W14 ^g	W16	W20	W24/ EOSI/ WD ^c	FU W2	FU W4	FU W8	FU W12	FU W16	FU W20	FU W24	FU W28	FU W32	FU W36	FU W40	FU W44	FU W48 /EOS /WD ^c		
Study Day (Window)	28 to 0	1	15 +/- 2d	29 +/- 2d	57 +/- 2d	85 +/- 2d	99 +/- 3d	113 +/- 3d	141 +/- 3d	169 +/- 3d	15 +/- 4d	29 +/- 4d	57 +/- 4d	85 +/- 4d	113 +/- 4d	141 +/- 4d	169 +/- 4d	197 +/- 4d	225 +/- 4d	253 +/- 4d	281 +/- 4d	309 +/- 4d	337 +/- 4d		
Provide PegIFN α2a self injection tracker ^f :																									
Arm 1		X				X																			
Arm 2						X																			
Arm 3		X																							
Review PegIFN α2a self injection tracker ^f :																									
Arm 1			At every study visit																						
Arm 2			At every study visit																						
Arm 3			At every study visit																						
Study intervention accountability ^o			X	X	X	X	X	X	X	X	(X)	(X)	(X)	(X)	(X)	(X)	(X)	(X)	(X)	(X)	(X)	(X)	(X)	(X)	
Assess NA treatment completion criteria ^{p,ww}											X	(X)													
Continuous assessment of NA re treatment criteria, as applicable ^o												(X)	(X)	(X)	(X)	(X)	(X)	(X)	(X)	(X)	(X)	(X)	(X)	(X)	
Safety Assessments																									
Complete physical examination ^s	X									X															
Body weight and symptom directed physical examination		X	X	X	X	X	X	X	X		X	X	X	X	X	X	X	X	X	X	X	X	X	X	
Ophthalmologic examination (including fundoscopy) ^t	X				X				X																
Vital signs ^u	X	X	X	X	X	X	X	X	X	X	X	X	X	X	X	X	X	X	X	X	X	X	X	X	
Triplicate 12 lead ECG ^v	X	X		X		X				X		X													
Injection site reactions (for JNJ 3989 and/or PegIFN α2a)		X	X	X	X	X	X	X	X	X	X														
Liver ultrasound		(X) ^w								X							X						X		
Medical resource utilization ^x	X	X	X	X	X	X	X	X	X	X	X	X	X	X	X	X	X	X	X	X	X	X	X	X	
Clinical Laboratory Tests																									
Hematology ^y	X	X	X	X	X	X	X	X	X	X	X	X	X	X		X	X			X			X	X	
Blood chemistry (including cystatin C and liver function tests) ^{z,aa,bb}	X	X	X	X	X	X	X	X	X	X	X	X	X ^{cc}	X	X ^{cc}	X ^{cc}	X	X ^{cc}	X ^{cc}	X	X	X	X	X	
Blood coagulation	X	X	X	X	X	X	X	X	X	X	X	X		X			X			X			X	X	
Urinalysis ^{dd}	X	X	X	X	X	X	X	X	X	X	X ^{ee}	(X)	(X)	(X)	(X)	(X)	(X)	(X)	(X)	(X)	(X)	(X)	(X)	X	
Urine chemistry ^{ff}	X	X	X	X	X	X	X	X	X	X	X ^{ee}	(X)	(X)	(X)	(X)	(X)	(X)	(X)	(X)	(X)	(X)	(X)	(X)	X	
Renal biomarkers ^{gg}		X				X				X															

Study Period	Screening	Treatment ^{a,b,c}									Follow-up ^{a,c,d}													

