- dd. Urinalysis by dipstick: specific gravity, pH, glucose, protein, blood, ketones, bilirubin, urobilinogen, nitrite, leukocyte esterase, and microscopic analysis if needed. The dipstick reading should be done as soon as possible and in accordance with the manufacturer's recommendation. In case of a positive dipstick result, a urine sample will be set aside for additional examination of the positive parameter (eg, quantification as applicable).
- ee. A urinalysis and urine chemistry sample will be taken at FU Week 2. In case of abnormalities, the tests should be repeated at the following visits.
- ff. Urine chemistry sample (quantitative measurement): creatinine, sodium, phosphate, glucose, protein, and albumin.
- gg. Urine sample for selected renal biomarkers including retinol binding protein and beta 2 microglobulin (other biomarkers might be measured).
- hh. For postmenopausal women only: An FSH level in the postmenopausal range may be used to confirm a postmenopausal state in women not using hormonal contraception or hormonal replacement therapy. However, in the absence of 12 months of amenorrhea, a single FSH measurement is insufficient to confirm a woman is not of childbearing potential (see Section 10.5, Appendix 5, Contraceptive and Barrier Guidance).
- ii. Additional samples may be collected for AFP testing in case of ALT flares.
- jj. Urine pregnancy tests should be done at least every 4 weeks, preferably during a scheduled site visit. Given the less frequent follow up of participants who continue NA treatment or have restarted NA treatment during the follow up period (provided that their HBV DNA and ALT values are stable), pregnancy tests for at home use may be provided to these participants from Follow up Week 4 onwards to allow 4 weekly urine pregnancy testing in between scheduled site visits. Participants will report the results to the study site personnel at the next visit, and these will be added to the source documents. If positive, the participant should contact the site immediately.
- kk. Only applicable to participants who are enrolled at a site with access to a Fibrosan device. A Fibrosan assessment will only be done at baseline if it was not done at screening.
- ll. HBV genotype will be determined at baseline using a standard genotyping assay if HBV DNA levels are sufficiently high. Available historical data on a previous HBV genotype assessment will also be collected in the CRF. Exploratory genotyping may be performed.

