#### Proteinuria by Urinalysis (Dipstick)

Treatment-emergent proteinuria by urinalysis (dipstick) over time will be summarized by intervention arm. Cross-tabulation of grades overtime versus baseline will also be presented.

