#### Phosphate excretion

Other renal biomarkers include FEPO4 that will be summarized by intervention arm and visit using descriptive statistics.

FEPO4 will be calculated as follows:

- Based on unadjusted serum creatinine:  

$$\text{FEPO4 (\%)} = (\text{SCr} \times \text{UPO4}) / (\text{SPO4} \times \text{UCr}) \times 100 (\%)$$

Where SCr is serum creatinine concentration, UPO4 is urine phosphate concentration, SPO4 is serum phosphate concentration, and UCr is urine creatinine concentration.

The proportions of participants with FEPO4  $\leq 10\%$  and  $>10\%$  will be tabulated.

The baseline, post-baseline, and change from baseline in FEPO4 will be summarized by intervention arm and visit using descriptive statistics. Median (Q1, Q3) change from baseline in FEPO4 over time will be plotted by intervention arm.

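### Urine tests from FU Week 4 to FU Week 44 are repeated only after an abnormal result, but the SAP summarises them by visit as if the whole arm were sampled, so the follow-up renal time course cannot be interpreted

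*SAP*

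**What the plan says.** **Sampling (Protocol 1.3, Schedule of Activities).** Urinalysis and urine chemistry carry a plain X at screening and through Week 24. Footnote ee governs what follows: "A urinalysis and urine chemistry sample will be taken at FU Week 2" and then "In case of abnormalities, the tests should be repeated at the following visits". The later follow-up cells in both rows are bracketed, except the last cell, which is a plain X. That cell reads as FU Week 48/EOS. FU Week 4 to FU Week 44 is 11 of the 13 scheduled follow-up visits.

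**Analysis (SAP).**
- 5.6.3.1, all laboratory tests: "Descriptive statistics and graphical displays will be presented for all chemistry, hematology, and urinalysis laboratory tests at scheduled time points".
- 5.6.3.2, renal parameters: descriptive statistics "for observed values and changes from baseline at each scheduled time point by intervention arm and analysis phase", with mean plots over time.
- 5.6.3.2.2, protein and albumin ratios: "The number and proportion of participants with UACR and UPCR results in the following categories over time will be tabulated", with median percent change plotted over time.
- 5.6.3.2.2, dipstick: "Treatment-emergent proteinuria by urinalysis (dipstick) over time will be summarized by intervention arm".
- 5.6.3.2.2, phosphate excretion: "Other renal biomarkers include FEPO4 that will be summarized by intervention arm and visit using descriptive statistics".

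None of these sections mentions the conditional repeat, limits the visits or names a denominator. The general safety rule in SAP 5.6 asks only for counts and percentages.

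**The concern.** A by-visit proportion or mean is read as the state of the arm at that visit. From FU Week 4 to FU Week 44 the people contributing urine data are there because an earlier urine result was abnormal. Numerators, means, medians and changes from baseline at those visits all describe that selected group, while the adjacent columns (Week 24, FU Week 2) describe everyone attending.

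This matters because the kidney is the one toxicity target organ that Protocol 2.2.2.2 names as shared by JNJ-3989 and the tenofovir products, and SAP 5.6.2 lists renal complications among the events of special interest. Whether tubular or protein findings resolve after treatment stops is the question these follow-up columns appear to answer. With the plan as written, a change from FU Week 2 to FU Week 4 could reflect the sampling rule alone.

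**Working it through.** The documents give no figure for this point, so there is nothing to reproduce. The check sets the sampling rule against the planned tables and then asks which way the tabulated rate moves when the true rate does not.

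**Step 1: do the conditional results enter the tables?** SAP 5.1.3 allocates all visits, for all assessments, to an analysis time point, and Table 4 has a window for every follow-up visit from FU Week 4 to FU Week 48. A repeat urine result therefore falls into a by-visit column unless a rule removes it, and there is none.

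**Step 2: one arm in whole numbers.** Take 34 participants, of whom 6 are abnormal at FU Week 2: 6/34 = 17.6%. All 6 are retested and 3 are still abnormal.
- Denominator those tested: 3/6 = 50.0%.
- Denominator the arm: 3/34 = 8.8%.
- If the true rate is unchanged, 3 of the 28 untested participants are newly abnormal and the truth is still 6/34 = 17.6%. Neither tabulated figure shows it.

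**Step 3: a range.** These inputs are assumptions and are not in the documents:
- t, share of the arm with any triggering urine abnormality at FU Week 2: 10%, 20%, 30%, 50%.
- a, share of those who have the abnormality being tabulated: 33%, 67%, 100%.
- q, probability that it persists at the next visit: 25%, 50%, 80%.

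The true rate is held at p = t × a, which fixes new onset at r = p(1 − q)/(1 − p). Then:
- rate among those tested = a × q + (1 − a) × r
- rate over the full arm, untested counted as not abnormal = t × (rate among those tested)

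| t | a | q | True rate | Among tested | Over full arm |
|---|---|---|---|---|---|
| 10% | 100% | 50% | 10.0% | 50.0% | 5.0% |
| 20% | 67% | 50% | 13.4% | 36.1% | 7.2% |
| 30% | 33% | 25% | 9.9% | 13.8% | 4.1% |
| 50% | 100% | 25% | 50.0% | 25.0% | 12.5% |

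First row: p = 0.10 × 1.00 = 0.10; among tested = 1.00 × 0.50 = 0.50; full arm = 0.10 × 0.50 = 0.05.

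Over all 36 combinations, the rate among those tested exceeds the true rate in 32, with ratios from 0.5 to 8.1. With a = 100% it rises only if q > t. The full-arm rate falls in all 36, to between 0.25 and 0.88 of the true rate.

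**Step 4: how many people.** With t between 10% and 30%, those tested number 34 × 0.10 = 3.4 to 34 × 0.30 = 10.2, or about 3 to 10 per arm of 34.

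**Step 5: other limits on the same columns.** Schedule footnote d makes FU Weeks 8, 16, 20, 28, 32, 40 and 44 optional for participants who continue or have restarted NA with stable values, so attendance also depends on NA status. FEPO4 needs serum creatinine and serum phosphate (SAP 5.6.3.2.2), but footnote cc limits blood chemistry to liver tests at FU Weeks 8, 16, 20, 28 and 32. It cannot be computed from scheduled samples there, even in retested participants. Retinol binding protein and beta-2-microglobulin are scheduled only at Day 1, Week 12 and Week 24 and are not affected.

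**The case against.** Several objections have weight.

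- **Direction is not fixed.** A reader might infer that abnormality rates must jump after FU Week 2 in every arm. The documents do not support that. No denominator is stated. With the full arm as denominator the rate falls, and even among those tested it fails to rise in 4 of the 36 combinations. Footnote ee also does not say which abnormality triggers a repeat. The dipstick and urine chemistry panels include items such as nitrite, ketones and sodium, so a retested participant may have normal protein ratios. This stands.
- **No magnitude can be quoted.** Prevalence and persistence are not in the documents. When every retested participant has the tabulated abnormality, the rate among those tested is simply the assumed persistence. This stands.
- **Other analyses limit the harm.** SAP 5.6.3.2 reports n, so a drop to a few participants would be visible. SAP 5.6.3.1 also gives worst-case abnormalities by phase, and the tubulopathy definition uses confirmed abnormalities, for which repeats are useful. This reduces the consequence but does not correct the by-visit summaries.
- **The rule is the same in all arms, and safety is descriptive.** A reader might infer that between-arm comparisons are systematically biased. The documents do not show this. At FU Week 4 to 44 those comparisons rest on small selected groups, and the main damage is to comparison over time.
- **Conditional repeats might not count as scheduled time points.** The SAP does not say so, and its visit windows would place them there.

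**Conclusion.** The point holds. From FU Week 4 to FU Week 44, urine results come from participants selected for an abnormal finding, and the SAP summarises them by visit on observed data with no restriction or stated denominator. Those columns do not estimate the arm's renal status, and the follow-up time course built from them is not interpretable. Abnormality rates are probably inflated if those tested are the denominator and understated if the full arm is. The size cannot be derived from the documents, and the figures above are illustrations under assumed prevalence and persistence.

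Two wider readings should be avoided. Not every visit after FU Week 2 is conditional: FU Week 48 appears to be sampled in everyone still in the study and would then be comparable with Week 24 and FU Week 2 apart from dropout. That reading comes from the last cell of both urine rows, and the extracted rows seem to carry one cell more than the header, so it must be checked against the original table. Nor is FEPO4 available at every follow-up visit, because of the visits with liver tests only.

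**What to change.** In SAP 5.6.3.1 and 5.6.3.2:

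1. Limit by-visit tables and plots of urinalysis, urine chemistry, UPCR, UACR and FEPO4 to visits with unconditional sampling: baseline, the treatment visits applicable to each arm, FU Week 2 and FU Week 48. Note that Week 2 applies to Arms 1 and 3 only and Week 14 to Arm 2 only. Confirm FU Week 48 against the original schedule first.
2. State that the denominator is participants tested at the visit.
3. Report the conditional FU Week 4 to 44 results as a listing and as resolved or persisted among participants abnormal at FU Week 2.
4. Keep those results in the worst-case and confirmed-abnormality analyses.

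The cost is SAP wording and fewer follow-up visits in the by-visit tables. Data collection does not change.
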